Protocol Number:	OPP-101
Investigational Product:	OC-01 (varenicline) Nasal Spray: 
 • 0.6 mg/mL • 1.2 mg/mL
Study Objective:	The objective of this study is to evaluate the safety and effectiveness of OC-01 (varenicline) Nasal Spray as compared to placebo on signs and symptoms of dry eye disease (DED)
Treatment Assignment	750 subjects will be randomized in a 1:1:1 into one of three treatment groups: 
 • 0.6 mg/mL • 1.2 mg/mL • Placebo (vehicle)
Sample Size and Power	
Randomization and Stratification	The randomization will be performed by a centralized IWRS system with three stratification factors: 
 • Pre-procedure (Baseline) anesthetized Schirmer's score (≤ 5, >5) measured at the screening/randomization visit. • Pre-procedure (Baseline) EDS (<60, ≥ 60) measured at the screening/randomization visit. • Study Site

Efficacy Endpoint	
Primary Endpoint:
 
• Percentage of subjects who achieve ≥ 10 mm improvement in Schirmer's Test Score from baseline at Visit 4 (Day 28) 
Secondary Endpoints
 
• Mean change from Baseline in Eye Dryness Score (EDS) in the study eye at 5 minutes after threshold defined treatment administration in the Controlled Adverse Environment Chamber at Week 4 (Visit 4a)• Mean change from Baseline in Eye Dryness Score (EDS) in the study eye at Week 4 (Visit 4b)• Mean change from Baseline in Schirmer's Test Score (STS) in the study eye at Week 4 (Visit 4b)• Mean change from Baseline in Inferior Corneal Fluorescein Staining in the study eye at Week 4 (Visit 4b)• Mean change from Baseline in Eye Dryness Score (EDS) in the study eye at Week 2 (Visit 3)• Mean change from Baseline in Eye Dryness Score (EDS) in the study eye at Week 1 (Visit 2)• Mean change from Baseline in Nasal Corneal Fluorescein Staining in the study eye at Week 4 (Visit 4b)• Mean change from Baseline in Temporal Corneal Fluorescein Staining in the study eye at Week 4 (Visit 4b)• Mean change from Baseline in Central Corneal Fluorescein Staining in the study eye at Week 4 (Visit 4b)• Mean change from Baseline in Superior Corneal Fluorescein Staining in the study eye at Week 4 (Visit 4b)• Mean change from Baseline in Total Corneal Fluorescein Staining in the study eye at Week 4 (Visit 4b) 
Page 7 of 34

--------------------------	---

Statistical Analysis for Primary Endpoint	
The primary efficacy endpoint will be analyzed on the ITT population using a [REDACTED] test comparing each of the treatment groups to placebo controlling for the randomization strata (study site, Baseline Schirmer's Test Score and Baseline EDS).

Multiplicity	
[REDACTED]
 
[REDACTED]

Analysis Populations	
The intent-to-treat (ITT) population will include all randomized subjects. Analyses using the ITT population will group subjects according to the treatment to which they were randomized.

2 Abbreviations

AE	adverse event
ANCOVA	analysis of covariance
BCVA	best corrected visual acuity
BID	twice daily
CAE®	Controlled Adverse Environment®
CMH	Cochran-Mantel-Haenszel
CFR	Code of Federal Regulations
eCRF	Electronica case report form
CI	confidence interval
CRF	case report form
DED	dry eye disease
EDS	Eye Dryness Score
FDA	Food and Drug Administration
HIPAA	Health Information Portability and Accountability Act
IB	Investigator's Brochure
ICF	informed consent form
ICH	International Conference on Harmonization
IRB	institutional review board
ITT	intent-to-treat
logMAR	logarithm of the minimum angle of resolution
LS	least square
MAD	mucosal atomization device
MAR	missing at random
MCAR	missing completely at random
MedDRA	medical dictionary for regulatory activities
MI	multiple imputation
MMRM	mixed model for repeated measures
MNAR	missing not at random
µL	microliter
mm	millimeter
nAChR	nicotinic acetylcholine receptor
OSDI©	Ocular Surface Disease Index©
PP	per protocol
SAE	serious adverse event
SAP	Statistical Analysis Plan

SD Standard deviation
STS Schirmer's Test Score
TEAE treatment-emergent adverse event
US United States

3 Introduction

This statistical analysis plan (SAP), which is based on the original protocol of the study protocol dated [REDACTED] defines the methods and analyses that Oyster Point Pharma, Inc. (henceforth, Oyster Point) plans to use to analyze the data from Protocol OPP-101. This SAP complies with guidance promulgated by the International Conference on Harmonization (ICH) and the US Food and Drug Administration (FDA). If the protocol is subsequently amended, this SAP may be amended as well. Should the SAP and the protocol be inconsistent with respect to the planned analyses, the language of the SAP prevails.

4 Study objective

The objective of this study is to evaluate the safety and effectiveness of OC-01 (varenicline) Nasal Spray as compared to placebo on signs and symptoms of dry eye disease (DED).

5 Study Design

This is a Phase 3, multicenter, randomized, controlled, double-masked study designed to evaluate the safety and efficacy of OC-01 (varenicline) Nasal Spray in adult participants with DED. Approximately 750 subjects at least 22 years of age with a physician's diagnosis of dry eye disease and meeting all other study eligibility criteria will be randomized to receive an application of OC-01 (varenicline) Nasal Spray or placebo twice daily (BID) for 28 days with three additional long-term follow-up visits at 6 weeks, 6 months and 12 months.

The three treatments are:

- Placebo (vehicle) [control]
- OC-01 (varenicline) Nasal Spray, 0.6 mg/mL
- OC-01 (varenicline) Nasal Spray, 1.2 mg/mL

Subjects who terminate early during the study period will be asked to complete safety assessments (if the subjects agree) prior to study exit. Subjects who are terminated early from the study will not be replaced.

Appendix 1 describes the detailed study visits, measurements, and dosing information.

6 Primary and Secondary Endpoints

6.1 Primary Efficacy Endpoint

The primary endpoint is percentage of subjects who achieve ≥ 10 mm improvement in the study eye on Schirmer's Test Score (STS) from baseline at Visit 4 (Day 28).

6.2 Secondary Efficacy Endpoints

There are 11 secondary efficacy endpoints:

[figure not shown]
1. Mean change from Baseline in Eye Dryness Score (EDS) in the study eye at 5 minutes after threshold defined treatment administration in the Controlled Adverse Environment Chamber at Week 4 (Visit 4a)
2. Mean change from Baseline in Eye Dryness Score (EDS) in the study eye at Week 4 (Visit 4b)
3. Mean change from Baseline in Schirmer's Test Score (STS) in the study eye at Week 4 (Visit 4b)
4. Mean change from Baseline in Inferior Corneal Fluorescein Staining in the study eye at Week 4 (Visit 4b).
5. Mean change from Baseline in Eye Dryness Score (EDS) at Week 2 (Visit 3)
6. Mean change from Baseline in Eye Dryness Score (EDS) at Week 1 (Visit 2)
7. Mean change from Baseline in Nasal Corneal Fluorescein Staining in the study eye at Week 4 (Visit 4b)
8. Mean change from Baseline in Temporal Corneal Fluorescein Staining in the study eye at Week 4 (Visit 4b)
9. Mean change from Baseline in Central Corneal Fluorescein Staining in the study eye at Week 4 (Visit 4b)
10. Mean change from Baseline in Superior Corneal Fluorescein Staining in the study eye at Week 4 (Visit 4b)
11. Mean change from Baseline in Total Corneal Fluorescein Staining in the study eye at Week 4 (Visit 4b)

6.3 Other Efficacy Endpoints

- The listed primary and secondary endpoints in the fellow eye
- The listed primary and secondary endpoints combining data from both study and fellow eyes

7 Sample Size Determination and Power Calculation

Approximately 750 subjects will be randomized into a 1:1:1 ratio to the three treatment groups. Approximately 250 subjects in each treatment group are expected to complete their assigned treatment and have endpoint assessments at Visit 4.

8 Statistical Hypothesis Testing

The null hypothesis for the primary endpoint is to test equality of the percentage of subjects who have $\geq 10\text{mm}$ change from baseline to Visit 4 in STS between the active drug-treated subjects and the placebo-treated subjects.

$H_0: P_l - P_p = 0$ vs. $H_1: P_l - P_p \neq 0$

or

$H_0: P_h - P_p = 0$ vs. $H_1: P_h - P_p \neq 0$

where P_l , P_h , and P_p denote the percentage of subjects in each group (low dose, high dose, and placebo, respectively) who have $\geq 10\text{mm}$ change from baseline to Visit 4 in STS.

9 Statistical Analysis

9.1 General Consideration

Descriptive and inferential statistics will be used to summarize results of Protocol OPP-101. Continuous variables will be summarized using the number of subjects (n), mean, SD, median, 25th and 75th percentiles, and minimum and maximum. Categorical variables will be summarized using frequency counts and percentages. Baseline measures will be defined as the last measure prior to the initiation of study treatment, usually at Visit 1 screening.

All summaries for safety data and efficacy data will be presented by treatment group. For the baseline characteristics, all summaries will be presented by treatment group and overall. All collected data will be presented in listings which will be sorted by treatment, subject ID, and visit when it is appropriate. Summaries, data listings, and statistical analyses will be generated using SAS® Version 9.4 or higher.

9.2 Analysis Populations

9.2.1 Intention-to-treat (ITT) population

The ITT population will include all randomized subjects. Analyses using the ITT population will group subjects according to the treatment to which they were randomized.

9.2.2 Per-protocol (PP) population

The PP population will include all subjects in the ITT population with post-baseline (Visit 1) data, excluding subjects who have major protocol deviations. Major protocol deviations will be identified prior to database lock by the sponsor. Analyses using the PP population will group subjects according to the treatment to which they were treated.

9.2.3 Safety population

The safety population will include all randomized subjects who received at least one dose of the study drug. Analysis of the safety population will group subjects according to the treatment actually received.

9.3 Unit of Analysis

For efficacy endpoints, the unit of analysis will be the study eye as defined as the eye that meets all inclusion and exclusion criteria. If both eyes qualify, then the study eye will be the eye with the greatest increase in tear production with stimulation by a cotton swab at the Screening Visit. If there is no difference in stimulated tear production, the study eye will be the eye with the lower Schirmer's Test Score at screening. If there is no difference for either measure, the right eye will be used as the study eye.

For safety endpoints, both eyes will be analyzed.

9.4 Definition of Study Day or Dosing Day

Study and dosing days are defined as follows:

Study Day = [Event date – Randomization date + 1] if after randomization
[Event date – Randomization date] if before randomization

Dosing Day= [Event date – First dosing date + 1] if after first dosing date
[Event date – First dosing date] if before first dosing date.

Note that with the definition above, days of "0" will not be used.

For subjects whose reference date is missing, the study day will also be categorized as missing.

9.5 Missing and Partial Data

[Redacted text block]

9.6 Protocol Deviations

[Redacted text block]

9.7 Data Handling with Mis-stratified Subjects

Subjects are randomized through an IWRS system with 3 stratification factors:

1. Pre-procedure (Baseline) anesthetized Schirmer's score (<5, >5) measured at the screening/randomization visit.

2. Pre-procedure (Baseline) EDS (<60, >60) measured at the screening/randomization visit.
3. Study Site.

Subjects may be mis-stratified for the baseline STS or baseline EDS in the IWRS. The analyses using the ITT and PP populations will follow the stratification factor to which each subject was categorized in the IWRS system. A sensitivity analysis using the corrected stratification factor may be performed as a related analysis.

9.8 Subject Disposition

The number and percentage of subjects randomized and included in each analysis population will be summarized by treatment and overall. Reasons for excluding subjects from the analysis populations will be presented in a by-subject listing.

The number of randomized subjects who completed the study, discontinued early from study drug, and reasons for discontinuation will be summarized by treatment group and overall. The Case Report Form (CRF) lists the following reasons why subjects may discontinue treatment before completing of the study:

- Non-fatal adverse event (AE)
- Protocol violation
- Lost to follow-up
- Pregnancy
- Physician decision
- Subject non-compliance
- Death
- Study terminated by sponsor
- Withdrawal by subject
- Other reasons

9.9 Demographics and Baseline Characteristics

Continuous variables will be summarized using the number of subjects (n), mean, SD, median, 25th and 75th percentiles, and minimum and maximum. Categorical variables will be summarized using counts and percentages. Summary data will be presented by treatment group and overall.

The following demographic and baseline characteristics will be summarized: age, gender, ethnicity, race, and ocular history.

Age in years will be calculated as the integer portion of the following:
 $[(\text{Date of informed consent} - \text{Date of birth}) + 1] / 365.25$.

Other baseline measurements, such as baseline visual acuity, will be summarized by treatment group.

9.10 Medical, Ocular and Dry Eye History

Medical history terms and ocular history terms will be coded using the Medical Dictionary for Regulatory Activities (MedDRA) version 22.0 and the number and percent of subjects with medical history will be summarized by (SOC) and Preferred Term (PT) for each treatment group based on the safety population.

In addition, the duration of ocular history and dry eye history will be summarized by treatment group and overall.

9.11 Treatment Exposure

Each randomized subject will receive an application of OC-01 (varenicline) Nasal Spray or placebo twice daily (BID) for 28 days. Duration of exposure to study treatment, in days, will be summarized for all randomized subjects. Summary statistics for duration of exposure will be presented by visit and treatment group.

10 Ocular Assessments

[figure not shown]
Ocular assessments will occur at baseline and post-baseline study visits. The results, grade, clinical significance, and relatedness to administration procedure and study drug, will be listed, summarized in tables, and presented in figures as appropriate.

10.1 Schirmer's Test

The Schirmer's Test with topical anesthetic will be performed to assess tear production at the Screening Visit (Visit 1). This first Schirmer's Test, which should be performed after corneal fluorescein staining, will be used as the baseline Schirmer's Test score. A second anesthetized Schirmer's Test with nasal stimulation using cotton swab will occur 10 minutes after the first anesthetized Schirmer's Test. Additional Schirmer's Tests with topical anesthetic will be assessed after the first treatment at Visit 1. At Week 2 (Visit 3), Week 4 (Visit 4b), the Schirmer's Tests will be performed concurrent with treatment.

10.2 Eye Dryness Score (EDS)

The Eye Dryness Score (EDS) will be assessed using a Visual Analog Scale (VAS). Subjects score EDS at Screening (Visit 1), Day 7 (Visit 2), Week 2 (Visit 3), Week 4 (Visit 4; pre-CAE®), Week 4 in the CAE® chamber (Visit 4a; pre-treatment followed by post-treatment

every 5 minutes within the CAE[®] for a total of 120 minutes), Week 4 (Visit 4b), and Early Termination (if necessary). At Visit 4, EDS from multiple time points and change in EDS from pre- to post-treatment will be collected and summarized by CAE exposure period and by treatment group. Participants will be asked to rate their ocular symptoms (both eyes simultaneously).

Some subjects did not meet the criterion of receiving a study drug during CAE[®] exposure (Ocular Discomfort score ≥ 3 at two or more consecutive time points in at least one eye during CAE[®] exposure). For such subjects, the EDS collected during CAE[®] exposure will be treated as missing and the EDS prior to entering CAE[®] will be carried forward to impute the missing EDS during CAE[®] exposure.

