10.4 Ocular Discomfort Scale

The  Ocular Discomfort Scale (ODS) will be collected at Screening (Visit 1) and Week 4 (Visit 4a; pre-CAE and post-CAE). Subjects will grade themselves on the ODS with scores from 0 to 4 to indicate the level of discomfort: 0 corresponds to “No discomfort”, 1 to “Intermittent awareness”, 2 to “Constant awareness”, 3 to “Intermittent discomfort”, and 4 to “Constant discomfort”. The ODS collected at Visit 4a will be used to determine treatment administration. Treatment of study drug will be administered when a participant reports an ODS ≥ 3 at two or more consecutive time points in at least one eye during CAE exposure (subjects with an ODS of 3 at time 0 for an eye must report an ODS of 4 for two consecutive measurements for that eye) using the Ora Calibra Scale. ODS will be summarized by visit, pre-CAE and every 5 minutes in CAE at Visit 4, and treatment group for both study and fellow eyes.

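### Do the study-eye, fellow-eye and combined-eye versions of the Eye Dryness Score distort the symptom analysis, given that the score appears to be a single rating?

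*SAP*

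**What the plan says.** The SAP's statements on EDS and the unit of analysis do not fit together exactly.

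- **How EDS is rated.** SAP 10.2: "Participants will be asked to rate their ocular symptoms (both eyes simultaneously". That section plans EDS summaries by chamber exposure period and treatment group, and does not mention study or fellow eye.
- **Endpoint wording.** SAP 6.2, item 2: "Mean change from Baseline in Eye Dryness Score (EDS) in the study eye at Week 4 (Visit 4b"; item 1 also names the study eye. Item 5 does not: "Mean change from Baseline in Eye Dryness Score (EDS) at Week 2 (Visit 3"; nor does item 6. The SAP synopsis gives the same Week 2 endpoint as "Mean change from Baseline in Eye Dryness Score (EDS) in the study eye at Week 2 (Visit 3", and attaches the study eye to all four EDS endpoints.
- **Unit of analysis.** SAP 9.3: "For efficacy endpoints, the unit of analysis will be the study eye". No exception is made for EDS. Protocol 10.5.2 has the same rule.
- **Further analyses.** SAP 6.3 adds "The listed primary and secondary endpoints in the fellow eye" and "The listed primary and secondary endpoints combining data from both study and fellow eyes". Again EDS is not excepted.
- **Contrast.** For the Ocular Discomfort Scale, SAP 10.4 says: "ODS will be summarized by visit, pre-CAE and every 5 minutes in CAE at Visit 4, and treatment group for both study and fellow eyes".

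The protocol's own EDS endpoints (6.1.2 and 10.1) name no eye. Where the two documents disagree, the SAP prevails.

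**The concern.** If EDS is one rating covering both eyes, there is no separate fellow-eye score. Taken literally, SAP 6.3 then asks for the same number under a second label, and for a combined analysis in which each subject's score could enter twice. Two things would be at stake. A fellow-eye result that agrees by construction might be read as corroboration. And a combined analysis with two identical rows per subject, treated as independent, would give intervals that are too narrow and too many false positives. EDS is the trial's symptom measure and supplies 4 of the 11 secondary endpoints (items 1, 2, 5 and 6), including the first two listed, so the point deserves a check.

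**Working it through.** **Inputs.** Protocol 10.4 gives an EDS difference of about 12 units, SD about 26, 250 subjects per arm and power of about 99% for each dose. Two-sided alpha of 0.05 is an assumption, because no visible text states it; 0.025 was also tried.

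**1. Reproduce the plan's figure.** SE of a difference in means = 26 × √(2/250) = 2.33. Then 12 / 2.326 = 5.16, and power ≈ Φ(5.16 − 1.96) = 99.9%. With two-sided 0.025 it is 99.8%. Both agree with the stated figure. The calculation uses one value per subject.

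**2. One score per subject, analysed sensibly.** Let y be the subject's change in EDS.
- Study eye: y. Fellow eye: y. The two analyses are identical.
- Average of the eyes: (y + y)/2 = y, so the SE stays at 2.33.
- Both rows kept, with clustering by subject: the within-subject correlation is 1, so the design effect is 1 + (2 − 1) × 1 = 2. The 500 rows per arm count as 500/2 = 250, and the SE is again 2.33.

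None of these routes changes the estimate, the interval or the error rate.

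**3. One score per subject, stacked as independent rows.** SE = 26 × √(2/500) = 1.64, a ratio of 1/√2 = 0.707, or 29% too small. The true two-sided error of a nominal 5% test is 2 × (1 − Φ(1.96/√2)) = 16.6%. A simulation of 20,000 two-sample t-tests on duplicated data also gave 16.6%.

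**4. Where that could occur.** SAP 6.3 adds two versions (fellow, combined) of each of the 4 EDS endpoints: 4 × 2 = 8 analyses per dose. Step 3 can apply only to the 4 combined ones. All 8 fall under other efficacy endpoints. The visible headings of Table 1 in SAP 12 show only primary and secondary endpoints in the testing order.

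**5. The other reading.** The sentence in SAP 10.2 could instead mean that each eye is scored at the same moment. Protocol 8.3.1 treats EDS and the Ocular Discomfort Scale together as the symptom assessments in the chamber, and the latter is rated by eye. The missing eye split in SAP 10.2 does not settle it: SAP 10.1 has none for Schirmer's test either, although protocol Appendix 2 places a strip in each eye. The part of Appendix 2 that would describe the EDS instrument cannot be read in the public copy. If EDS is scored by eye, the study-eye wording is right, the fellow-eye analyses carry information, and only the sentence in SAP 10.2 is loose.

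**The case for a change.** The best case for acting is that the SAP prevails over the protocol, that its text is inconsistent under either reading of EDS, and that the inconsistency touches the two secondary endpoints listed first. Correcting it would cost a few words, and a reader of the final tables might take matching study-eye and fellow-eye results as mutual support.

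The inconsistency stands: SAP 6.2 and the synopsis do not even agree on which EDS endpoints name the study eye. The harm does not follow. The inflated error rate needs a particular method, duplicate rows treated as independent, which no visible text specifies. SAP 12.1, 12.2 and Appendix 2, where methods would be given, are blacked out, and they cannot be presumed to omit subject-level averaging or clustering. The same answers any request for a clustered method for Schirmer's test and corneal staining. As for false corroboration, a fellow-eye EDS table that matches the study-eye table in every digit shows itself to be a duplicate.

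**Conclusion.** The concern is right about the wording, but no change to the plan follows. If EDS is one score per subject, the phrase about the study eye has no effect on the four secondary EDS endpoints: whichever eye is named, the value is the same, the SE is 2.33 and power is 99.9%. The extra fellow-eye and combined-eye versions are then redundant tables among the other efficacy endpoints, and an analyst holding one score per subject will see that at once. If EDS is scored by eye, those versions are legitimate. The 16.6% error rate is a conditional illustration. It assumes a single score, stacking without allowance for the subject, and a two-sided 5% test; even then it stays outside the primary and secondary tests. This rests on the planning values in protocol 10.4 and on the visible headings of Table 1. What remains is a clerical slip that alters no primary or secondary result.

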10.3 BCVA

Best corrected visual acuity (BCVA) will be performed and collected at Screening (Visit 1), Day7 (Visit 2), Week 2 (Visit 3), Week 4 (Visits 4a (pre-CAE) and 4b), and Early Termination (if necessary). Visual function of the study and fellow eye will be assessed starting at 10 feet using the best corrected ETDRS protocol. Visual acuity examiners must be certified to ensure consistent measurement of BCVA. In order to provide standardized and well-controlled assessments of visual acuity during the study, all visual acuity assessments at a single site must be performed consistently using the same lighting conditions and same correction, if possible, during the entire study. If the same correction cannot be used (e.g., a subject broke his/her glasses), the reason for the change in correction should be documented. BCVA will be summarized by visit and by treatment group for both study and fellow eyes.

